E-mail : [contact]

Medical monitor:

[name] [name]., F.A.C.P.
Clinical Professor, Emeritus
UCB-UCSF Joint Medical Program
Chair, Editorial Board, UC Berkeley *Wellness Letter*
University of California, Berkeley
[name]
[contact]
[contact]
E-mail: [contact]

STUDY SYNOPSIS

Name of sponsor company: California Department of Public Health (CDPH)	
Name of investigational product: Recombinant Botulinum Vaccine A/B (rBV A/B)	
Names of active ingredients: Recombinant Botulinum Antigen A and Antigen B adsorbed to 0.2% (wt/vol) Alhydrogel™	
Title of study: Tolerability and Immunogenicity of a Single 40- μ g Dose of Recombinant Botulinum Vaccine A/B (rBV A/B) for the Production of BabyBIG® in Volunteers with Existing Botulinum Immunity	
Sponsor Investigator: [name]	
Number of sites: 2	
Study period: 18 months	Phase of development: Phase 2
Objectives:	
Immunogenicity: The immunogenicity objective of this study is to evaluate the effects of a single 40- μ g dose of the recombinant botulinum vaccine A/B (rBV A/B) on botulinum toxin type A and type B neutralizing antibody concentration (NAC) over a 12-week period following vaccination in participants who have previously been immunized with pentavalent botulinum toxoid (or pentavalent botulinum toxoid and rBV A/B) for occupational protection.	
Safety: The safety objective of this study is to obtain safety information during the 12-week study period and at 6 months post-vaccination on the use of rBV A/B in a population of participants previously immunized with pentavalent botulinum toxoid (or pentavalent botulinum toxoid and rBV A/B) for occupational protection.	
Exploratory: The exploratory objective of this study is to collect source plasma from participants that contains neutralizing antibodies against botulinum toxin type A and type B for the production of BabyBIG .	
Methodology: This Phase 2, open-label, uncontrolled study designed to evaluate safety, tolerability, and immunogenicity of a single dose of rBV A/B in healthy participants previously immunized with pentavalent botulinum toxoid (or pentavalent botulinum toxoid and rBV A/B) for occupational protection will be conducted to collect source plasma for potential use in the production of BabyBIG and to evaluate safety and immunogenicity of the vaccine in these participants over a 12-week period, with a follow-up safety assessment at 6 months.	
The study period is defined as the 12-week period that includes the clinic visits and plasmapheresis visits. The study period will end at Week 4 for participants who opt not to participate in plasmapheresis or who have been determined to be ineligible for plasma donation for the entire study.	
Number of participants (planned): Up to 50 participants are anticipated to be enrolled.	

STUDY SYNOPSIS (continued)

Name of sponsor company: California Department of Public Health (CDPH)
Name of investigational product: Recombinant Botulinum Vaccine A/B (rBV A/B)
Names of active ingredients: Recombinant Botulinum Antigen A and Antigen B adsorbed to 0.2% (wt/vol) Alhydrogel™
Inclusion criteria:

 • Have received pentavalent botulinum toxoid (or pentavalent botulinum toxoid and rBV A/B) for occupational protection under BB-IND-0161 (or BB-IND-0161 and IND 015155) • Be 18 to 69 years old at the time of consent • Be healthy and have an acceptable medical history (defined as individuals who are free from significant cardiac, pulmonary, gastrointestinal, hepatic, renal, hematological, neurological, infective, muscular, infectious, rheumatic, immunological, or psychiatric diseases, as determined by medical history over the past 5 years, physical examination, and laboratory tests) that will not interfere with the objectives of the study • Meet the participant suitability requirements and recommendations for source plasma donors • If female and of childbearing potential, have a negative pregnancy test at screening and within 24 hours prior to vaccination and must not plan to become pregnant for until after the last plasma donation or until the Week 12 visit (whichever occurs last). Every female participant is considered of childbearing potential unless she has had sterilization surgery or is postmenopausal and has not had a menstrual period for at least 12 months. If the participant is capable of childbearing, she must use a reliable form of contraception approved by the investigator for 30 days before Day 0 through the end of the study. Acceptable forms of contraception include intrauterine device, birth control pills, injectable birth control, implantable birth control device, or removable birth control device or any other United States Food and Drug Administration (U.S. FDA) -approved contraceptive method, or a monogamous relationship with vasectomized partner who has been vasectomized for 6 months or more prior to the participant's study entry, or sexual abstinence.) • Have the ability to understand the requirements of the study, have provided written informed consent as evidenced by signature on an informed consent form approved by the Committee for the Protection of Human Subjects, and have agreed to abide by the study restrictions and return for the required assessments • Agree to complete the participant home diary on a daily basis for 7 days post-vaccination, as well as report any adverse events and concomitant medications during the study period • Have provided written authorization for use and disclosure of protected health information • Agree not to donate blood or blood products (outside of study procedures) until after the last plasma donation or until the Week 12 visit (whichever occurs last) • Have personal health insurance
Exclusion criteria:

 • Be pregnant or nursing • Have a history of laboratory evidence of syphilis, acquired immunodeficiency syndrome, Creutzfeldt-Jakob disease, or infection with human immunodeficiency viruses 1 or 2, human T-cell lymphotropic virus 1, hepatitis B virus, or hepatitis C virus • Have had a prior severe (Grade 3 or higher) local or severe (Grade 3 or higher) systemic reaction to last immunization with pentavalent botulinum toxoid or a prior severe immediate hypersensitivity reaction or severe systemic reaction to last vaccination on Day 0 with rBV A/B • Have a known allergy to aluminum compounds, yeast, or other components of the vaccine • Have donated one or more units of blood or undergone plasmapheresis within 49 days prior to the Vaccination Visit (Day 0)

STUDY SYNOPSIS (continued)

Name of sponsor company: California Department of Public Health (CDPH)
Name of investigational product: Recombinant Botulinum Vaccine A/B (rBV A/B)
Names of active ingredients: Recombinant Botulinum Antigen A and Antigen B adsorbed to 0.2% (wt/vol) Alhydrogel™

 • Have received a blood product or immunoglobulin within 6 months of study entry or plans to receive such products during the study period (exclusive of returned red blood cells as part of the plasmapheresis procedure). For participants who choose to donate plasma, this will apply until their last plasma donation or at the Week 12 visit (whichever occurs last) • Have received licensed nonliving vaccine within 14 days prior to study entry, or licensed live vaccine within 60 days prior to study entry • Have received investigational products (drugs, biologics, vaccines, or implantable devices) within 60 days prior to study entry or plans to receive experimental products at any time during the study period. For participants who choose to donate plasma, this will apply until their last plasma donation or at the Week 12 visit (whichever occurs last) • Have received prescription immunosuppressive or immunomodulatory agents, including parenteral, inhaled, or oral corticosteroids within 3 months of study entry or plans on receiving such therapy at any time during the study period. For participants who choose to donate plasma, this will apply until their last plasma donation or at the Week 12 visit (whichever occurs last) with the exceptions mentioned below: 
 ○ Participants who have used prescription topical steroids may be enrolled 2 weeks after the therapy is completed ○ Intra-articular, bursal, or tendon injectable steroids are permitted ○ Any over-the-counter topical steroid use is permitted ○ Ophthalmic and intranasal steroids are permitted • Have received cytotoxic therapy at any time in the previous 5 years before study entry • Have an active systemic or recurrent disease that would place the participant at unacceptable risk of injury, require hospitalization, or require surgical intervention (This includes active mental illness or history of mental illness not responsive to treatment.) • Have a history of alcohol or drug abuse or dependence within 12 months of study entry • Have past, present, or suspected illicit injection drug use • Have inflammatory, vasculitic, or rheumatic disease, including systemic lupus erythematosus, polymyalgia rheumatica, rheumatoid arthritis, or scleroderma (Stable osteoarthritis treated with physical therapy and nonsteroidal anti-inflammatory drugs is not an exclusion criterion.) • Have any acute or chronic neuromuscular or neurologic disorder • Have clinically confirmed hepatic or renal insufficiency • Have uncontrolled hypertension, as defined as systolic blood pressure greater than 160 mmHg and diastolic blood pressure greater than 90 mm Hg • Have moderate to severe asthma, chronic obstructive pulmonary disease, or other significant pulmonary disease • Have a seizure disorder • Have moderate or severe illness or oral temperature of 100.4°F or greater within 3 days prior to Vaccination Visit (Day 0) • Be unsuitable for participation in this study for any reason, as assessed by the investigator

STUDY SYNOPSIS (continued)

Name of sponsor company: California Department of Public Health (CDPH)
Name of investigational product: Recombinant Botulinum Vaccine A/B (rBV A/B)
Names of active ingredients: Recombinant Botulinum Antigen A and Antigen B adsorbed to 0.2% (wt/vol) Alhydrogel™
Test product, dose, and mode of administration: rBV A/B injections will consist of 40- μ g of total antigen (20 μ g of Antigen A and 20 μ g of Antigen B) adsorbed to 0.2% (wt/vol) Alhydrogel™, in a total dose volume of 0.5 mL. The vaccine will be administered by intramuscular injection in the deltoid muscle, preferably in the nondominant arm.
Reference therapy, dose, and mode of administration: No reference therapy will be employed.
Duration of treatment: Vaccine administration for all enrolled participants will occur at Day 0, and participants may elect to undergo plasmapheresis up to two times a week for up to 12 weeks, with the final on-site visit at Week 12 (\pm 4 days) and follow-up phone call for safety assessment at Week 26 after vaccination. Participants can elect to continue plasmapheresis up to 14 weeks post-vaccination as long as long as they continue to meet source plasma donor eligibility requirements..
Criteria for Evaluation
Populations: The immunogenicity population will include all participants who have received the study vaccine at the assigned dosage and for whom at least one post-baseline NAC was collected within 4 weeks of vaccination. For each post-vaccination assessment time point, the per protocol population will include all participants who received the vaccine dose, have a baseline NAC, and have all immunogenicity assessments completed within the protocol-specified timelines (including visit windows) for the time periods summarized and do not have major protocol violations expected to affect immunogenicity. A determination of major protocol violations expected to affect immunogenicity will be done by the sponsor-investigator before reviewing the immunogenicity data for the applicable participant.
Immunogenicity: The primary endpoint is as follows: 
• The proportion of participants achieving a four times or greater increase in NAC by Week 4 compared with Week 0. A positive response will be defined as achieving this level of increase in at least 50% of the participants for botulinum toxin A and toxin B. The secondary endpoints are as follows: 
• The proportion of participants achieving a two times increase in the area under the plasma concentration-time curve between Week 0 and Week 12 in NAC in comparison to a straight-line extension of the Week 0 NAC to Week 12. A positive response will be defined as achieving this level of increase in at least 50% of the participants for botulinum toxin A and toxin B.• The proportion of participants achieving a three times or greater increase in NAC by Week 4 compared with Week 0. A positive response will be defined in at least 50% of the participants for botulinum toxin A and toxin B.
Safety: Safety analyses will be performed on the safety population, defined as all participants who receive the investigational vaccine. The following analyses will be performed:

STUDY SYNOPSIS (continued)

Name of sponsor company: California Department of Public Health (CDPH)
Name of investigational product: Recombinant Botulinum Vaccine A/B (rBV A/B)
Names of active ingredients: Recombinant Botulinum Antigen A and Antigen B adsorbed to 0.2% (wt/vol) Alhydrogel™

• Frequency of injection site reactions and systemic reactions in the study population that are characterized as severe or result in a serious adverse event (SAE) during the 0-7 day diary collection period.• Frequency of injection site reactions and systemic reactions that are characterized as serious adverse events (SAEs).• Participant incidence of treatment-related SAEs.• Participant incidence of serious new onset chronic illnesses (NOCIs).• Clinically significant changes from baseline health that result in an SAE.• Clinically significant changes in hematology between screening and Week 4 that result in a severe or serious AE.
Exploratory: The exploratory endpoint will be the volume of source plasma containing neutralizing antibodies against botulinum toxin type A and type B collected by plasmapheresis for use in BabyBIG manufacture.

STUDY SYNOPSIS (continued)

Name of sponsor company: California Department of Public Health (CDPH)
Name of investigational product: Recombinant Botulinum Vaccine A/B (rBV A/B)
Names of active ingredients: Recombinant Botulinum Antigen A and Antigen B adsorbed to 0.2% (wt/vol) Alhydrogel™
Study design: This will be an open-label, uncontrolled study to evaluate the safety and immunogenicity of a single 40- μ g intramuscular injection of rBV A/B in participants who were previously immunized with pentavalent botulinum toxoid (or pentavalent botulinum toxoid and rBV A/B) for occupational protection. Participants will receive the rBV A/B injection, and undergo plasmapheresis up to two times per week for up to 14 weeks. Participants will be evaluated for safety and immunogenicity at each study visit with follow-up safety data collected at 6 months. If participants opt not to participate in plasma collections or have been determined to be ineligible to donate plasma for the entire study, they will have a final on-site visit at Week 4 to provide a serum sample for NAC determination and an additional hematology specimen. Participants undergoing plasmapheresis will also have an additional hematology specimen collected at Week 4. Study participants participating in plasma donations will have a final on-site study visit at Week 12. All participants will have a final phone call for safety follow-up at Week 26.
Experimental procedures: Participants who meet inclusion criteria and do not meet any exclusion criteria will receive a single rBV A/B injection at Week 0 and will complete a 7-day diary for the Week 1 telephone call. Clinical safety laboratory assessments (serum chemistry, hematology, and urinalysis) will be obtained for all participants at the screening visit. Hematology only will be assessed during the Week 4 visit. Study participants who consent to plasma donation may report to the plasma collection center after the Week 1 visit where they will be assessed by the center for donor eligibility. Once donor eligibility has been confirmed, the participant may choose to donate plasma twice a week for up to 14 weeks.
Safety considerations: Participants will be monitored for serious adverse events after vaccination throughout the 12-week study period and at the Week 26 phone call follow-up. Administration site reactions and systemic reactions will be monitored with a diary provided to collect information, including diameter of any swelling and redness around the injection site and any generalized symptoms between Week 0 and Week 1 in order to determine if any severe reactions or serious adverse events occurred during this 1-week period post-vaccination. All severe local and systemic reactions will be recorded in the electronic case report form (eCRF). Hematology, serum chemistry, and urinalysis specimens will be collected at screening, and repeat hematology at Week 4 for monitoring of any clinically significant changes that result in a severe or serious AE. Clinically significant changes in hematology that result in a severe or serious AE will be recorded on the eCRF. Female participants of childbearing potential will have a urine pregnancy test at screening and again at Week 0 prior to receipt of the vaccine. Source plasma collection will occur for eligible donors at licensed collection locations. If the participant fails to meet donor criteria at any time during the plasmapheresis period, the participant will continue to be followed for serious adverse events according to the study schedule. Participants will be contacted by phone at Weeks 1, 4, and 10. At Week 26, participants will be queried for occurrence of serious adverse events and serious new onset chronic illnesses (NOCIs), which will be recorded by the investigator (or designee) on serious adverse events recording sheets and entered in the eCRF. Vital signs will be monitored at screening, Week 0 (vaccine visit), and at each plasma collection visit.

STUDY SYNOPSIS (continued)

Name of sponsor company: California Department of Public Health (CDPH)
Name of investigational product: Recombinant Botulinum Vaccine A/B (rBV A/B)
Names of active ingredients: Recombinant Botulinum Antigen A and Antigen B adsorbed to 0.2% (wt/vol) Alhydrogel™
Statistical methods: The data will be summarized in tables listing the mean, standard deviation or standard error, median, minimum, maximum, and number of participants for continuous data, or in tables listing count and percentage for categorical data, where appropriate.
The immunogenicity parameters are NACs for botulinum toxin type A and type B. These NAC parameters will be analyzed utilizing a validated mouse neutralization assay.
Summaries of local and systemic severe AEs and SAEs related to vaccination (collected in the 7-day diaries) will be produced in tables, by category and severity.
Summaries of clinically significant changes in hematology between screening and Week 4 resulting in a severe or serious AE will be listed.
SAE data will be listed individually and summarized by system organ class and preferred terms and by severity and relatedness.
SAE data of NOCIs will be listed individually and summarized by system organ class and preferred terms and by severity and relatedness.
No formal sample size calculations will be done.

TABLE OF CONTENTS

	Page
TITLE OF STUDY:	1
1.0 INTRODUCTION.....	16
1.1 BACKGROUND.....	16
1.2 STUDY RATIONALE.....	17
1.3 DOSE RATIONALE	17
2.0 OBJECTIVES	19
2.1 IMMUNOGENICITY	19
2.2 SAFETY.....	19
2.3 EXPLORATORY	19
3.0 STUDY DESIGN.....	20
3.1 BASIC DESIGN CHARACTERISTICS	20
3.2 STUDY POPULATION	20
3.2.1 Inclusion Criteria	20
3.2.2 Exclusion Criteria	22
3.3 ENDPOINTS	24
3.3.1 Immunogenicity.....	24
3.3.2 Safety.....	25
3.3.3 Exploratory	25
3.4 RANDOMIZATION AND BLINDING	26
3.5 REPLACEMENT OF DROPOUTS.....	26
4.0 DRUGS AND DOSAGES	27
4.1 IDENTIFICATION AND DESCRIPTION OF INVESTIGATIONAL PRODUCT	27
4.1.1 Investigational Product	27
4.1.2 Labeling	28
4.2 DOSING INSTRUCTIONS AND SCHEDULE.....	28
4.3 STORAGE AND HANDLING OF INVESTIGATIONAL PRODUCT	29
4.4 DOSE STOPPING RULES.....	29
4.4.1 Individual Participant Stopping Rules	29
4.4.2 Study Stopping Rules	29
4.5 CONCOMITANT MEDICATIONS	30
5.0 EXPERIMENTAL PROCEDURES.....	31
5.1 OVERVIEW: SCHEDULE OF TIME AND EVENTS	31
5.2 MEASUREMENTS AND EVALUATIONS.....	34
5.2.1 Screening Period (between Days -7 and -1)	34
5.2.2 Treatment Period (12 weeks, plasma donors; 4 weeks non-plasma donors)	35
5.2.3 Final Study Follow-up (Day 182, Week 26).....	40
6.0 PROCEDURES FOR HANDLING SERIOUS ADVERSE EVENTS.....	41
6.1 DEFINITION OF A SERIOUS ADVERSE EVENT	41
6.2 RECORDING SERIOUS ADVERSE EVENTS	42

TABLE OF CONTENTS (continued)

	Page
6.3 ASSESSMENT OF SEVERITY	43
6.4 ASSESSMENT OF CAUSALITY.....	44
6.5 EXPECTEDNESS OF ADVERSE EVENTS	46
6.6 REPORTING OF SERIOUS ADVERSE EVENTS	46
6.7 FOLLOW-UP OF SERIOUS ADVERSE EVENTS	48
6.8 LOCALIZED AND SYSTEMIC INJECTION SITE REACTIONS	48
6.9 DATA AND SAFETY MONITORING BOARD	49
6.10 PREGNANCY	49

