5.0 EXPERIMENTAL PROCEDURES

5.1 OVERVIEW: SCHEDULE OF TIME AND EVENTS

For this clinical trial there is a 7-day screening period (Days -7 to -1) in which participant eligibility will be determined. Participants will enter either a 4-week (non-plasma donors) or a 12-week (plasma donors) treatment period in which a single rBV A/B injection will be administered on Day 0 to stimulate the production of antibodies against botulinum toxin type A and type B. Participants will be able to donate plasma starting 1 week after injection with rBV A/B at a frequency of up to two times a week, for up to 12 weeks with the possibility of extending the donation times up to 14 weeks post-vaccination in accord with FDA plasma donation regulations and guidelines.^[2] NAC sample collections are required for all participants at Week 0 and Week 4. NAC sample collection is required for plasma donors with each donated unit. Safety assessments for non-plasma donors are scheduled on Week 0, Week 1 (by phone), and Week 4 (final on-site visit). Safety assessments for plasma donors are at Week 0 with follow-up phone calls at Weeks 1, 4 and 10, and a final on-site study visit at Week 12 to assess general health status and query for the interim occurrence of any SAEs or NOCIs. All participants will have a final phone call for safety follow-up at Week 26. Concomitant medications will be queried for at each study visit. Any concomitant medication used to treat a severe injection site or systemic reaction from Week 0-1 as well as any SAEs or serious NOCIs throughout the study will be recorded in the eCRF.

The schedule of events is presented in [Table 1](#).

Table 1. Schedule of Time and Events

Measurements/Evaluations	Screening	Vaccination Visit	Telephone Call	Study Period	Telephone Call	Plasmapheresis	Final Study Visit	Follow-up Call
	Day -7 to -1	Week 0, Day 0	Week 1 ^a	Week 4 ^{a, b}	Week 10 ^a	Week 2- 14 ^c	Week 12 ^d	Week 26 ^e
Informed consent	X					X ^f		
Physical examination	X					X ^g		
Medical history	X							
Prior medication history	X							
Urine pregnancy test	X	X ^h					X	
Inclusion/exclusion criteria	X	X						
Vital signs	X	X ⁱ				X		
Informed consent for plasma collection	X							
HIV, HBV, and HCV tests ^j						X		
Hematology	X ^k			X ^l				
Serum chemistry	X ^k							
Urinalysis	X ^k							
NAC sample collection		X ^m		X ⁿ		X	X	
Plasmapheresis ^o						X		
rBV A/B injection		X						
Injection site evaluation		X ^p		X			X	
Diary distribution ^q		X						

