Diary review			X					
Serious adverse event collection ^r		X	X	X	X		X	X
Concomitant medication information	X ^t		X ^s	X ^s	X ^s		X ^s	X ^s
Phone call			X	X	X			X

HBV = hepatitis B virus; HCV = hepatitis C virus; HIV = human immunodeficiency virus; NAC = neutralizing antibody concentration; rBV A/B = recombinant botulinum vaccine A/B.

a. Week 1, Week 4, and Week 10 Follow-up Calls must occur with ± 3 days of the scheduled time.

b. Final Study Visit will be an on-site visit at Week 4 for participants who opt not to participate or who have been determined to be ineligible for donation for the entire study. All final assessments occurring at Week 12 will occur at Week 4 for these participants.

c. Extension of plasmapheresis for up to 14 weeks is optional

- d. Final on-site Study Visit must occur within \pm 7 days of the scheduled time.
- e. Final follow-up call for safety must occur within \pm 1 week of the scheduled time.
- f. Plasmapheresis-specific informed consent formed will be signed at the source plasma center.
- g. Physical examination will be performed as part of source plasma donor screening at the plasma collection center
- h. Female participants of childbearing potential must have a negative pregnancy test within 24 hours prior to vaccination.
- i. Participants will have vital signs taken twice at Visit 1: prior to injection, and 30 minutes (\pm 5 minutes) after receiving the injection.
- j. HIV, HBV, and HCV tests will be performed on each donated source plasma unit
- k. Results from screening tests must be available before Vaccination Visit
- l. Study participants will go to central lab or plasma center for this draw (not an on-site visit).
- m. Baseline NAC sample must be collected before rBV A/B injection and before plasmapheresis
- n. Participants not donating plasma must go to site for NAC collection within \pm 3 days of the scheduled time.
- o. May occur up to twice a week for up to 14 weeks (if hemoglobin and total protein remain within acceptable range) following vaccination with rBV A/B.
- p. At this visit, participants will be monitored for at least 30 minutes after injection for a possible reaction.
- q. In the diaries, participants record adverse events in order to determine SAE, oral temperature and injection site information.
- r. Only serious adverse events and new onset chronic illnesses are to be queried for and collected

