5.2.2.5 Telephone Calls (Weeks 4 and 10)

Study personnel will call plasma donating participants at Weeks 4 (\pm 3 days) and 10 (\pm 3 days) to inquire about participants overall well-being, SAEs, if any, that occurred since the last visit or phone call, any concomitant medication used, any NOCIs, any AEs that increased in severity and injection site or systemic reactions. SAEs, including serious NOCIs, serious injection site or systemic reactions and concomitant medication used as treatment will be recorded in the eCRF.

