APPENDIX E

ADVERSE EVENT RECORDING SHEET FOR IDENTIFICATION OF POSSIBLE SERIOUS ADVERSE EVENTS (SAES)

Tolerability and Immunogenicity of a Single 40- μ g Dose of Recombinant Botulinum Vaccine A/B (rBV A/B) for the Production of BabyBIG® in Volunteers with Existing Botulinum Immunity

Adverse Events Recording Sheet for Identification of Possible Serious Adverse Events (SAEs)

Study Site/Location*: _____ / _____ Participant Study ID Number*: _____

Participant Name: _____

Recombinant vaccine given: _____ Date: _____ / _____ / _____ Time: _____ AM / PM

- You may or may not experience any adverse events. The purpose of this recording sheet is for you to document at home any adverse events during the course of the study, if such should occur.
- If you make an error while recording, please draw a single line through the error, add your correction and initial. Please no white out or multiple lines through errors.
- The information you document on this form will be queried for by study staff during on-site study visits and phone call follow-up for safety at Weeks 1, 4, 10 and 26.
- Please indicate the date and time (if relevant) of each event's occurrence, as well as the date/time of the event's resolution.
- Please categorize the event's severity as indicated below.

Note: If you experience severe, life-threatening or any of the following neuromuscular symptoms (blurred or double vision, drooping of eyelids, drooping of the mouth, dry mouth, difficulty swallowing, difficulty speaking, weakness of an arm or leg, lack of coordination, shallow breathing, sensitivity to sunlight, or inability to perspire), **please seek medical attention immediately and notify [name] (24/7/365 [contact]) or [name] (24/7/365 [contact]) as soon as possible.**

*Please categorize the severity of the reaction as:

mild	= you are able to perform all routine daily activities
moderate	= you are able to perform some routine activities, but are limited in others
severe	= you are unable to perform all routine activities, often seeking medical care

#	Reaction or Event Description/Location	New Event? (Y/N)	Date / Time Started	Date / Time Ended	Severity	Treatment	Comments

Additional Comments, if any (please continue on reverse side).

* To be filled in by study staff

Ver. August 2018

Site Investigator's Initials _____

**Tolerability and Immunogenicity of a Single 40- μ g Dose of Recombinant
Botulinum Vaccine A/B (rBV A/B) for the Production of BabyBIG® in Volunteers

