1.6 STUDY PROCEDURES

The study will begin with a 7-day screening period (Days -7 to -1), during which participant eligibility will be determined. Screening must occur 1 to 7 days before the Vaccination Visit (Day 0).

Participants will enter either a 4-week treatment period (for non-plasma donors) or a 12-week treatment period (for plasma donors). At the Vaccination Visit (Day 0), the first day of the treatment period for all subjects, participant eligibility will be reviewed and blood collection will be performed to determine baseline NAC. After these assessments, a single rBV A/B injection will be administered to stimulate the production of antibodies against botulinum toxin type A and type B. Safety assessments will be performed before and after the injection, and a diary will be distributed to the participant to record injection site information, systemic reactions, and concomitant medications over the next seven days.

Study personnel will call all participants at Week 1 (\pm 3 days) to review the diary, injection site reactions, and any potential serious adverse events (SAEs) or new onset chronic illnesses (NOCIs) occurring over the past week.

Participants who receive the rBV A/B vaccination may elect to participate as source plasma donors if they meet the donor eligibility criteria of the sponsor-approved licensed source plasma collection site. Participants who elect to donate source plasma may begin following the Week 1 safety phone call and may donate up to twice per week through Week 12, with the possibility of continuing through Week 14 post-vaccination if they continue to meet source plasma donor eligibility criteria. The assessments to be completed at the visits to the plasma collection center are listed in the protocol and include a blood collection for NAC determination.

Safety assessments for non-plasma donors are scheduled on Week 0, Week 1 (\pm 3 days) (by phone), and Week 4 (\pm 3 days) (final on-site visit). Safety assessments for plasma donors are scheduled at Week 0 with follow-up phone calls at Weeks 1 (\pm 3 days), 4 (\pm 3 days) and 10 (\pm 3 days), and a final on-site study visit at Week 12 (\pm 7 days) to assess general health status and query for the interim occurrence of SAEs or NOCIs, if any.

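### The Week 10 safety call is for everyone in some places and for plasma donors only in others; on the donors-only text, non-donors have no scheduled safety contact for 154 days

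*Protocol*

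**What the plan says.** **No donor restriction on the Week 10 call**

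- Protocol Synopsis, Safety considerations: "Participants will be contacted by phone at Weeks 1, 4, and 10".
- Protocol Table 1: the Week 10 column marks SAE collection, concomitant medication and a phone call. Footnote a ("Week 1, Week 4, and Week 10 Follow-up Calls must occur with", then a tolerance of 3 days either way) names no subgroup. SAP Table 1 has the same column and footnote.
- Appendix E, the recording sheet given out at the vaccination visit, announces "phone call follow-up for safety at Weeks 1, 4, 10 and 26".

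**Donors only**

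- Protocol 5.1: "Safety assessments for non-plasma donors are scheduled on Week 0, Week 1 (by phone), and Week 4 (final on-site visit"). It lists the Week 10 call in the donor schedule.
- Protocol 5.2.2.5: "Study personnel will call plasma donating participants at Weeks 4" and 10.
- SAP 1.6 makes the same split: "Safety assessments for plasma donors are scheduled at Week 0 with follow-up phone calls at Weeks 1", 4 and 10.

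**Surrounding text**

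- Synopsis: "The study period will end at Week 4 for participants who opt not to participate in plasmapheresis". Protocol 3.1 and SAP 1.3 agree.
- Footnote b of both tables handles non-donors by moving the final visit: "All final assessments occurring at Week 12 will occur at Week 4 for these participants". It does not mention Week 10.
- The safety objective (Protocol 2.2) covers 12 weeks plus 6 months, and Protocol 3.3.2 has the primary safety endpoints collected over 12 weeks. Neither is limited to donors.
- All participants receive the Week 26 call, which asks about SAEs and serious NOCIs since the last contact (Protocol 5.2.3).

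**The concern.** A site working from Table 1 would phone a non-donor at Week 10, and a site working from 5.2.2.5 would not. Two sites are planned, so follow-up of non-donors could differ by site without either one deviating from the protocol. Non-donors also take home a sheet announcing a Week 10 call that 5.2.2.5 does not schedule for them.

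What is at stake is when an event becomes known. Under Protocol 4.4.2, one SAE judged at least possibly related to the vaccine halts all dosing. Under 6.7, the 24-hour reporting clock starts only when the investigator learns of the event. If a non-donor does not volunteer an SAE that occurs after Week 4, the next scheduled question about it comes at Week 26. Whether dosing would still be under way by then depends on the pace of enrolment, which the documents do not give.

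A related slip concerns the recording sheet. Protocol 5.2.2.1 issues it for seven days, while 5.2.2.3 has participants use it between calls and Appendix E has them use it throughout the study.

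**Working it through.** The plan states no figure for the contact gap, so there is none to reproduce. The inputs are scheduled days and windows.

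| Contact | Day | Window | Source |
|---|---|---|---|
| Week 4 visit (non-donors) | 28 | ±3 | Protocol 5.2.2.4 |
| Week 10 call | 70 | ±3 | Protocol 5.2.2.5, Table 1 footnote a |
| Week 12 visit (donors) | 84 | ±7 | Table 1 footnote d |
| Week 26 call (all) | 182 | ±7 | Protocol 5.2.3, Table 1 footnote e |

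**Step 1. Non-donor gap on the donors-only text**

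- Nominal: 182 − 28 = 154 days (22 weeks).
- Shortest: (182 − 7) − (28 + 3) = 144 days.
- Longest: (182 + 7) − (28 − 3) = 164 days.
- For comparison, the donors' longest nominal gap is Week 12 to Week 26: 182 − 84 = 98 days.

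**Step 2. Non-donor gaps if the Week 10 call is added**

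- Week 4 to Week 10: 70 − 28 = 42 days. Range (70 − 3) − (28 + 3) = 36 to (70 + 3) − (28 − 3) = 48.
- Week 10 to Week 26: 182 − 70 = 112 days. Range (182 − 7) − (70 + 3) = 102 to (182 + 7) − (70 − 3) = 122.
- The longest gap falls by 154 − 112 = 42 days, and 42/154 = 27%.

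**Step 3. Share of the 12-week (84-day) period first asked about at Week 26, for non-donors**

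- Donors-only text: 84 − 28 = 56 days; 56/84 = 67%.
- With the Week 10 call: 84 − 70 = 14 days; 14/84 = 17%.

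**Step 4. Endpoints to which Step 3 applies**

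Two of the six endpoints in Protocol 3.3.2 have observation windows that close by Week 4 for everyone: severe reactions over Days 0 to 7, and hematology changes from screening to Week 4. The percentages in Step 3 do not apply to these. They bear only on the endpoints that rest on SAEs and serious NOCIs.

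**Step 5. Number of participants affected**

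The documents do not give the number of non-donors. With up to 50 enrolled, it lies between 0 and 50. Inclusion criterion 4 requires everyone to meet source plasma donor suitability at entry, so 50 is a formal ceiling and not an expectation.

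**The case against.** The strongest reply is that donors only is what the plan means. The detailed procedural sections agree with one another, the treatment period in 5.2.2 is headed as 4 weeks for non-donors, and their study period is defined to end at Week 4. The synopsis sentence follows two sentences about plasma donation. It also lists a Week 4 phone call, which under 5.2.2.5 only donors receive, so it may be a loose summary of the donor schedule. Table 1 is a composite that also carries a plasmapheresis column.

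This makes donors only a plausible intent, and a reader should not infer that an all-participant call was clearly planned. It does not remove the conflict. Contact with non-donors continues after Week 4, since they receive the Week 26 call. The tables also mark non-donor exceptions elsewhere (footnotes b and n) but put none on Week 10.

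A second reply is that nothing is lost, and that is right. A reader might infer that non-donor SAEs between Week 4 and Week 26 go unrecorded, or that the safety tables are biased. The documents do not support either. SAP 8.1 records SAEs through the Week 26 call, and that call asks about interim events. Appendix E tells participants with severe, life-threatening or listed neuromuscular symptoms to seek care immediately and notify contacts available at all hours. The same sheet has columns for dates, severity and treatment, which limits recall error if it is kept up. The gap is in scheduled contact only.

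Third, extending the call does not fully cover the 12 weeks: 14 days would still be first asked about at Week 26. That also stands.

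**Conclusion.** The conflict is real, lies in the current text of both documents, and is minor. On the donors-only text, non-donors have no scheduled safety contact for 154 days (144 to 164), against 98 days for the longest nominal gap in donors. The consequence is later capture of SAEs and serious NOCIs in non-donors, more dependent on recall, together with contradictory site instructions. The Day 0 to 7 reaction endpoint, the Week 4 hematology endpoint and the immunogenicity analyses are unaffected.

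The day counts rest only on the stated schedule and windows. How many participants are affected, and whether dosing would still be open when a late-reported event surfaced, cannot be determined from the documents.

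**What to change.** **Preferred change**

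- In Protocol 5.1, Protocol 5.2.2.5 and SAP 1.6, extend the Week 10 call (±3 days) to non-donors. Describe it as safety follow-up after their final on-site visit, asking about SAEs, serious NOCIs and the medication used to treat them.
- In the synopsis, both Table 1s and Appendix E, note that the Week 4 contact is an on-site visit for non-donors and a call for donors. These places need this edit even though their Week 10 entry could then stay as it is.
- In Protocol 5.2.2.1, replace the seven-day limit on the recording sheet with use until the Week 26 call, in line with 5.2.2.3 and Appendix E.

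**If the sponsor intends donors only**

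Mark the Week 10 call that way in the synopsis, both Table 1s and Appendix E. Qualify Protocol 3.3.2 to say that non-donor safety after vaccination is ascertained at Weeks 1, 4 and 26. The 154-day gap then remains, but as a stated choice.

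**Cost**

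At most 50 short calls by existing staff, and only if every participant were a non-donor. There are no new visits or samples. Adding a scheduled safety contact may need handling as an amendment under Protocol 9.4, with ethics approval and regulatory submission.
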